4.4.3 Derived Other Variables

4.4.3.1 Years Elapsed since Priming Vaccination Received in Either MET50, MET43, or Outside of Sanofi Pasteur Trials

Years ($3 \leq \text{years} < 4$, $4 \leq \text{years} < 5$, or $5 \leq \text{years} \leq 6$) elapsed since priming vaccination is computed as follows: (Date of Vaccination in MET59 – Date of Vaccination in MET50, MET43, or outside of Sanofi Pasteur trials + 1) / 365.25

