3. Percentage of subjects with titer $\geq 1:8$ and $\geq 1:128$ and 95% CI
4. Percentage of subjects with titer ≥ 4 -fold rise from pre-vaccination to post-vaccination, and 95% CI
5. Percentage of subjects with rSBA vaccine seroresponse*

*rSBA vaccine seroresponse is defined as a post-vaccination titer $\geq 1:32$ for subjects with pre-vaccination rSBA titer $< 1:8$, or a post-vaccination titer ≥ 4 times the pre-vaccination titer for subjects with pre-vaccination rSBA titer $\geq 1:8$.

Data from subjects from MET50 (or MET43, if applicable) and MET59 will be combined and paired to evaluate antibody persistence and overall trends over 3-6 years post-priming with an MCV4 (ie, MenACYW conjugate vaccine-primed subjects or Menveo vaccine-primed subjects). If Menveo vaccine primed subjects that were not part of MET50 are recruited, those will not contribute to the assessment of antibody persistence.

Additional subgroup analyses of the hSBA vaccine seroresponse rates, hSBA titer $\geq 1:4$ and $\geq 1:8$, hSBA GMTs, rSBA vaccine seroresponse rates, rSBA titer $\geq 1:8$ and $\geq 1:128$, and rSBA GMTs will also be provided by number of years (3 years, 4 years, 5 years, and 6 years) elapsed since

priming vaccination received in either clinical studies MET50, MET43, or outside of Sanofi Pasteur trials, age group (13 to 17 years and 18 to 26 years), gender (Female and Male), and race (White, Asian, Black or African American, and Other).

Safety

Safety analysis will include but is not limited to the following:

1. The number and percentage of subjects reporting any solicited injection site reactions and solicited systemic reactions occurring from D0 to D07 after each vaccination will be summarized by study group for intensity, time of onset period, days of occurrence, and action taken. Since MenACYW conjugate vaccine and the concomitant MenB vaccines will be administered in different limbs, solicited injection site reactions can be distinguished between the two products, and will be analyzed and presented separately.
2. Immediate unsolicited systemic AEs and unsolicited AEs occurring up to D30 after each vaccination will be summarized.
3. The number and percentage of subjects reporting any unsolicited non-serious AEs will be summarized by study group, intensity, time of onset period, duration, and by MedDRA preferred term and system organ class (SOC), as well as by relationship to the study vaccine.

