4. The number and percentage of subjects reporting at least one of any MAAEs will be summarized throughout the trial.
5. The number and percentage of subjects reporting at least one of any SAEs will be summarized by study group, seriousness criterion, outcome, and by MedDRA preferred term and SOC, as well as by relationship to the study vaccine.
6. The number and percentage of subjects reporting at least one of any AESIs will be summarized throughout the trial.
7. Exact (Clopper-Pearson) 2-sided 95% CIs will be calculated for the percentages.

Additional subgroup safety analyses will also be provided by number of years (3 years, 4 years, 5 years, and 6 years) elapsed since priming vaccination received in either clinical studies MET50, MET43, or outside of Sanofi Pasteur trials, age group (13 to 17 years and 18 to 26 years), gender (Female and Male), and race (White, Asian, Black or African American, and Other).

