5.1.4 Complementary Output

Additional subgroup analyses by number of years ($3 \leqslant$ years < 4 , $4 \leqslant$ years < 5 , $5 \leqslant$ years $\leqslant 6$) elapsed since priming vaccination received in either clinical studies MET50, MET43, or outside of Sanofi Pasteur trials, age group (13 to 17 years and 18 to 26 years), gender (Female and Male), and race (White, Asian, Black or African American, and Other) will be provided in Appendix 15 of the CSR.

Demographics analyses by number of years since primed vaccines only:

- Baseline demographics – All Randomized or Assigned Subjects
- Baseline demographics – Per-Protocol Analysis Set 1
- Baseline demographics – Per-Protocol Analysis Set 2
- Baseline demographics – Safety Analysis Set

Immunogenicity analyses (tables and figures):

- hSBA GMTs and 95% CI at D0 and D30 for each group – Per-Protocol Analysis Set 2
- hSBA GMTs and 95% CI at D0 and D06 for Groups 1 and 2 – Per-Protocol Analysis Set 1
- Vaccine seroresponse against meningococcal serogroups A, C, Y, and W measured by hSBA and 95% CI at D30 for each group – Per-Protocol Analysis Set 2
- Vaccine seroresponse against meningococcal serogroups A, C, Y, and W measured by hSBA and 95% CI at D06 for Groups 1 and 2 – Per-Protocol Analysis Set 1
- hSBA titer $\geq 1:4$ and $\geq 1:8$ (vaccine seroprotection) against meningococcal serogroups A, C, Y, and W and 95% CI at D0 and D30 for each group – Per-Protocol Analysis Set 2
- hSBA titer $\geq 1:4$ and $\geq 1:8$ (vaccine seroprotection) against meningococcal serogroups A, C, Y, and W and 95% CI at D0 and D06 for Groups 1 and 2 – Per-Protocol Analysis Set 1
- rSBA GMTs and 95% CI at D0 and D30 for Groups 1 and 2 – Per-Protocol Analysis Set 2
- Vaccine seroresponse against meningococcal serogroups A, C, Y, and W measured by rSBA and 95% CI at D30 for Groups 1 and 2 – Per-Protocol Analysis Set 2
- rSBA titer $\geq 1:8$ and $\geq 1:128$ against meningococcal serogroups A, C, Y, and W and 95% CI at D0 and D30 in Groups 1 and 2 – Per-Protocol Analysis Set 2

Safety analyses:

Safety overview after injection – Safety Analysis Set

Analysis to assess the impact of COVID-19:

- To summarize the impact of COVID-19 on the overall study conduct
 - Early termination due to COVID-19
 - Impact on visit conduct (visit not done, partially done, data collection method/procedure change)
 - Major and critical protocol deviations due to COVID-19

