5.7 Changes in the Conduct of the Trial or Planned Analyses

The analysis set FAS3 is added in the SAP. FAS3 will be used to evaluate the antibody persistence 3-6 years after the priming vaccination with either MenACYW conjugate vaccine or the licensed vaccine Menveo®.

No other significant change occurred during the conduct of the trial not documented in a protocol amendment.

6 References List

4. Pollard AJ. Global epidemiology of meningococcal disease and vaccine efficacy. *Pediatr Infect Dis J*. 2004;23(12 Supp):S274-9.
5. European Centre for Disease Prevention and Control. Surveillance of invasive bacterial diseases in Europe 2008/2009. Stockholm: ECDC; 2011.
6. Centers for Disease Control and Prevention. Active Bacterial Core Surveillance (ABCs) Report: Emerging Infections Program Network. *Neisseria meningitidis*, 2013. Available at: <http://www.cdc.gov/abcs/reports-findings/survreports/mening13.html>. Accessed 23 September 2015.

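### The SAP's three time-since-priming strata leave subjects at or beyond six calendar years, or under three, with no stratum, and the move from the protocol's four subgroups is not recorded

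*SAP*

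**What the plan says.** Protocol 12.1.3 says the additional immunogenicity subgroup analyses "will also be provided by number of years (3 years, 4 years, 5 years, and 6 years) elapsed since" priming. It repeats the four categories for safety: "Additional subgroup safety analyses will also be provided by number of years (3 years, 4 years, 5 years, and 6 years) elapsed since priming vaccination". The synopsis carries the same list.

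SAP 4.4.3.1 defines three strata: 3 to under 4, 4 to under 5, and 5 to 6 with both ends included. The formula follows the words "elapsed since priming vaccination is computed as follows" and is ("Date of Vaccination in MET59 – Date of Vaccination in MET50, MET43, or outside of Sanofi Pasteur trials + 1) / 365.25". SAP 5.1.4 uses the same three strata for its "Additional subgroup analyses by number of years", which cover baseline demographics, hSBA and rSBA results and the safety overview, all directed to Appendix 15 of the study report. Neither section has a residual or out-of-range category.

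SAP 5.7 names the new analysis set FAS3 as a change and then states: "No other significant change occurred during the conduct of the trial not documented in a protocol amendment".

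On eligibility (Protocol 5.2.4), criterion 2 requires participation in and completion of MET50 or MET43 and sets no limit on time since priming. Only criterion 3, for the Group 2 enrichment population, asks for an interval of 3 to 6 years, and it does not define the upper end in days.

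**The concern.** The inclusive upper limit looks as if it was written to keep a subject at exactly six years, merging the protocol's 5- and 6-year categories. The formula in the same sentence does not allow that. Six years at 365.25 days is not a whole number of days, and the added day pushes the sixth anniversary over the limit.

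A subject with no stratum cannot be placed in any by-years table, so the strata need not add up to the analysis set. At the upper end these are the subjects with the longest interval since priming, the ones a waning-by-time display most needs. Because SAP 5.7 is silent, a reader comparing the report with the protocol would find a planned 6-year category missing without explanation.

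**Working it through.** The plan gives no figure of its own on this point, so the check applies the SAP's rule to dates.

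**Inputs**
- Formula and strata: SAP 4.4.3.1.
- D0 dates: the planned inclusion period in Protocol 5.1.5, 3 September 2019 to 2 March 2020, which is 182 calendar days.
- Priming dates: set at each anniversary before D0 and one day either side. Where D0 is 29 February and the earlier year has no such day, 1 March is used.

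**Upper limit in days**
- 6 × 365.25 = 2191.5. A whole-day count can never return exactly 6.
- The condition (difference + 1)/365.25 ≤ 6 requires a difference of at most 2190 days.
- Six calendar years are 6 × 365 = 2190 days plus one or two leap days, that is 2191 or 2192.
- (2191 + 1)/365.25 = 6.0014 and (2192 + 1)/365.25 = 6.0041. Both exceed 6.

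**Results over the 182 planned D0 dates**

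| Time since priming | Value from the SAP formula | No stratum |
|---|---|---|
| One day short of 3 years | 2.9979 or 3.0007 | 180 of 182 |
| Exactly 3 years | 3.0007 or 3.0034 | 0 of 182 |
| Exactly 4 years | 4.0027 | 0 of 182 |
| Exactly 5 years | 5.0021 or 5.0048 | 0 of 182 |
| One day short of 6 years | 5.9986 or 6.0014 | 2 of 182 (1 and 2 March 2020) |
| Exactly 6 years | 6.0014 or 6.0041 | 182 of 182 |
| One day past 6 years | 6.0041 or 6.0068 | 182 of 182 |

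Taking every priming date with six completed years (6 to under 7), 182 × 365 = 66,430 date pairs arise, and all 66,430 fall in no stratum.

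**Does removing the added day cure it?** No. Without it, the sixth anniversary gives 2191/365.25 = 5.9986 on 180 dates, which is classified, but 2192/365.25 = 6.0014 on the other 2, which is not. One day past the anniversary gives 6.0014 or 6.0041 and is unclassified on all 182.

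**Who could be affected?** At the upper end, a subject primed on or before the same calendar date six years before D0. Across the planned inclusion period that cut-off runs from 3 September 2013 to 2 March 2014. The documents give no MET50 or MET43 vaccination dates, so no count follows.

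**The case against.** The strongest reply is that the trial is described throughout, including in both primary objectives, as a study of people primed 3 to 6 years earlier. For that population a stratum of 5 to 6 years inclusive is a natural last category. It merges two labels that the protocol never defined in days, and merging is acceptable in itself. Within the described population, a separate completed-years category of 6 would hold little beyond the anniversary. One may add that the per-protocol set excludes subjects not vaccinated in the proper time window, and that SAP 5.7 speaks only of significant changes.

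Part of this stands. Merging is not the error, and whether it counts as significant is a matter of judgement. The rest does not remove the problem. The rule fails to deliver the merge, because the anniversary itself computes above 6. The 3-to-6-year description is not an eligibility limit for MET50 or MET43 subjects. The documents define no window between priming and booster, so it is unclear whether the per-protocol exclusion reaches this interval.

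Three stronger inferences are tempting, and the documents do not support them:
- **That these subjects are lost from the persistence or primary results.** They are not. No rule based on the strata removes anyone from the primary test, the secondary summaries, FAS3 or the overall safety analysis. Nor does the SAP say that unclassified subjects are discarded; it simply gives them no place in the by-years tables.
- **That a sizeable 6-year group is deleted.** Without source-study dates nothing shows that such a group exists.
- **That subjects just short of six years are widely affected.** Within the planned inclusion period this happens on 2 of 182 D0 dates.

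**Conclusion.** The point holds as a defect in a stated classification rule. Under SAP 4.4.3.1 and 5.1.4, every subject at or beyond six calendar years since priming has no stratum, and neither does a MET50 or MET43 subject under 3 years. The reduction from four protocol subgroups to three is not recorded in SAP 5.7.

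Its size is small. The number of subjects is unknown and may be zero, and the effect is confined to descriptive by-years outputs in an appendix. The conclusion takes six years to mean the calendar anniversary. The counts by date also assume D0 within the planned inclusion period, but the anniversary result itself does not depend on that: any six-year span with one or two leap days computes above 6.

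**What to change.** In SAP 4.4.3.1 and 5.1.4, open both end strata: under 4 years; 4 to under 5; 5 to under 6; and 6 or more. If the last cell is sparse, merge the last two into 5 or more. Every vaccinated subject with a known priming date then falls in exactly one stratum. With open ends the added day may stay, since it can only move a boundary case into the neighbouring stratum; removing it without opening the strata does not solve the problem.

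Add a line to SAP 5.7 stating how the strata differ from those in Protocol 12.1.3.

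The cost is SAP wording and one derivation line. No new data are needed.

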4.4.3.2 Race for Subgroup Analyses

Race for subgroup analyses will be categorized as:

- White
- Asian
- Black or African American
- Other

Note: The original race categories collected in CRF will still be used for demographics analyses. The American Indian or Alaska Native, Native Hawaiian or Other Pacific Islander, Mixed origin, Not Reported and Unknown will be classified to “Other” stratum for subgroup analysis purpose only.

4.4.3.3 Subject Duration

The duration of a subject in the study is computed as follows: Maximum (Date of last visit, Date of term form) – (Date of D0 Visit) + 1.

The duration of a subject in the study including follow-up is computed as follows: Maximum (Date of last visit, Date of term form, Date of last date of follow-up contact) – (Date of D0 Visit) + 1.

4.4.3.4 Duration of the Study

The duration of the study (until last visit) is computed as follows: Maximum of all subjects (Date of last visit, Date of termination form) – minimum for all subjects (Date of D0 Visit) + 1.

The duration of the study (including follow-up) is computed as follows: Maximum of all subjects (Date of last visit, Date of termination form, Date of last follow-up contact) – minimum for all subjects (Date of D0 Visit) + 1.

4.4.3.5 Protocol-prohibited Therapy, Medication or Vaccines

In general, the “prohibited” variable is not derived. All concomitant medications are reviewed by the clinical team and the value of “prohibited” variable is determined before database lock by the clinical team according to the following rules:

Only two categories of reportable medications will be considered as prohibited/restricted therapy, medication or vaccine:

Category 2:

- Flu vaccines administered within 14 days pre or post each trial vaccination, including the day of the study visit vaccination
- Other vaccines not included as study vaccines, it means non-study vaccines (e.g. Oral poliovirus, Yellow fever, Japanese encephalitis, or other routine/not-routine vaccine not described in the protocol) within the 28 days (4 weeks) preceding or after the trial vaccination, including the day of the study visit vaccination
- Immune globulins, blood or blood-derived products and Immunosuppressive therapy, as described in the protocol

Category 3:

- Antibiotics that the subject received within the 72 hours preceding each Visit for blood draw related to IMP assessment (meningococcal vaccines)

If the above protocol-prohibited therapy, medication or vaccines are received at specific visits, it will impact the corresponding immunogenicity analyses.

The impact on each Per-Protocol Analysis Set (PPAS) is determined as the following:

- If the above protocol-prohibited therapy, medication or vaccines are received at D0 or D06, it will impact PPAS1.
- If the above protocol-prohibited therapy, medication or vaccines are received at D0 or D30, it will impact PPAS2.

5 Statistical Methods and Determination of Sample Size

The statistical analyses will be performed under the responsibility of the Sponsor's Biostatistics platform using SAS® Version 9.4 software or later.

The results of the statistical analysis will be available in the final Clinical Study Report (CSR).

For descriptive purposes, the following statistics in [Table 5.1](#) will be presented. The confidence interval (CI) for the single proportion will be calculated using the exact binomial method (Clopper-Pearson method, quoted by Newcombe [\(14\)](#), ie, using the inverse of the beta integral with SAS®). The CI of the difference in percentages will be computed using the Wilson Score method without continuity correction [\(15\)](#).

For immunogenicity results, assuming that Log10 transformation of the titers / data follows a normal distribution, at first, the mean and the 95% CI will be calculated on Log10 (titers / data) using the usual calculation for normal distribution (using Student's t distribution with n-1 degree of freedom), then antilog transformations will be applied to the results of calculations, in order to provide geometric means and their 95% CI.

Table 5.1: Descriptive statistics produced

Baseline characteristics and follow-up description	Categorical data	Number of subjects Percentage of subjects
	Continuous data	Mean, standard deviation, quartiles, minimum, and maximum
Clinical safety results	Categorical data	Solicited: Number and percentage (95% CIs) of subjects Unsolicited: Number and percentage (95% CIs) of subjects, and number of events
Immunogenicity results	Categorical data (seroresponse, seroprotection, cutoff)	Number and percentage (95% CIs) of subjects
	Continuous data (titer / concentration)	Log10: Mean and standard deviation Anti-Log10 (work on Log10 distribution, and anti-Log10 applied): Geometric mean, and 95% CI of the geometric mean Graphical representation by Reverse Cumulative Distribution Curve (RCDC)

5.1 Statistical Methods

5.1.1 Hypotheses and Statistical Methods for Primary Objective

5.1.1.1 Hypotheses

Thirty days after the administration of MenACYW conjugate vaccine, the sufficiency of the percentages of subjects who achieve an hSBA seroresponse* for meningococcal serogroups A, C, Y, and W in Group 1 and Group 2 will be tested.

Seroresponse will be considered sufficient if lower limit of the 1-sided 97.5% CI calculated using the exact method (Clopper-Pearson method) for percentage of subjects with hSBA seroresponse against serogroups A, C, Y, and W is greater than 75%. The study will be considered successful if the seroresponse sufficiency is demonstrated both in Group 1 and Group 2 separately.

This is equivalent to testing $H_0: p \leq 0.75$ against $H_1: p > 0.75$, where p is the observed proportion of subjects with hSBA seroresponse against serogroups A, C, Y, and W.

*hSBA vaccine seroresponse for serogroups A, C, Y, and W is defined as follows:

- For a subject with a pre-vaccination titer $< 1:8$, the post-vaccination titer must be $\geq 1:16$
- For a subject with a pre-vaccination titer $\geq 1:8$, the post-vaccination titer must be at least 4-fold greater than the pre-vaccination titer

5.1.1.2 Statistical Methods

The CI for the single proportion will be calculated using the exact binomial method (Clopper-Pearson method, quoted by Newcombe (14), ie, using the inverse of the beta integral with SAS®).

5.1.2 Hypotheses and Statistical Methods for Secondary Objectives

5.1.2.1 Hypotheses

No hypotheses will be tested. Descriptive statistics will be presented.

5.1.2.2 Statistical Methods

5.1.2.2.1 For Secondary Objective 1

Six days after the administration of MenACYW conjugate vaccine, the hSBA vaccine seroresponse rates, seroprotection rates (hSBA titer $\geq 1:8$), and hSBA GMTs between a subset of 50 subjects per Group 1 and Group 2 will be summarized and geometric mean titer ratio (GMTR) between the subset of 50 subjects per Group 1 and Group 2 will be calculated, and 95% CI will be provided.

5.1.2.2.2 For Secondary Objective 2

Thirty days after the administration of MenACYW conjugate vaccine alone, the hSBA vaccine seroresponse rates, seroprotection rates (hSBA titer $\geq 1:8$), and the hSBA GMTs will be summarized and GMTR between Group 1 and Group 2 will be calculated, and 95% CI will be provided.

5.1.2.2.3 For Secondary Objective 3

Before the administration of MenACYW conjugate vaccine alone, 3-6 years after receiving the primary MCV4 vaccination, the hSBA GMTs will be summarized as well as seroprotection rates (hSBA titer $\geq 1:8$) and GMTR between Groups 1, 3, and 4 and Group 2 will be calculated, and 95% CI will be provided.

5.1.2.2.4 For Secondary Objective 4

At baseline and D30, in subjects after having received a single dose of either MenACYW conjugate vaccine or Menveo vaccine, as part of study MET50 or MET43, the hSBA GMTs will be summarized as well as seroprotection rates (hSBA titer $\geq 1:8$) and GMTR between MenACYW conjugate vaccine and Menveo vaccine groups will be calculated, and 95% CI will be provided. The GMTR between D0 of MET59 and D30 of MET50 (or MET43, if applicable) within MenACYW conjugate vaccine and Menveo vaccine groups will also be calculated, and 95% CI will be provided.

5.1.2.2.5 For Secondary Objective 5

Thirty days after the administration of MenACYW conjugate vaccine when administered alone or concomitantly with Trumenba vaccine or Bexsero vaccine, the vaccine seroresponse, seroprotection (hSBA titer $\geq 1:8$), and hSBA GMTs will be summarized and GMTR between Group 1 and Group 3, between Group 1 and Group 4, and between Group 1 and pooled Groups 3 and 4 will be calculated, and 95% CI will be provided.

